## **5 Statistical Analysis**

### **5.1 Data Summaries and Conventions**

All data collected on case report forms will be provided in listings, except data collected only for confirmation of study entry criteria and for study administrative purposes. If any enrolled patient is found to not have valid documented informed consent, that patient's data will be excluded from the report, except as necessary to document the error.

Except where specified all continuous variables will be summarized with descriptive statistics (the number of non-missing values, mean, standard deviation, median, minimum and maximum) and all categorical variables will be summarized with frequency counts and percentages, by part, treatment, and overall.

## **5.2 Missing Data**

For adverse events and concomitant medication, the imputation rule for start date and end date are defined in relevant sections (i.e., AE and subsequent therapies sections). For other analysis when necessary (e.g., OS analysis), dates without a specific day of the month (i.e., JAN2010) will be assigned the 15th day of the month and dates without a specific day or month (i.e., 2010) will be assigned the 15th day of June.

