- b Day 56 restaging CT or MRI scans should be performed if the optional treatment #9 is not given. If a PET CT is used, a standard high resolution CT series should be obtained rather than low resolution scans for tumor measurements. However, PET scans should not be used to determine disease progression since it is expected that PET avidity will increase with the type of inflammation induced by this treatment and may lead to false positive results. Confirmation of disease progression by CT or MRI must be performed 4 or more weeks later per IrRC. If the 9th dose is given, then CT/MRI should be delayed to Day 63 to 77. Photographs: if the tumor can be measured and assessed visually, photographic documentation with measurements should be considered in order to keep a record and help assess any response to treatment (may be performed at any time during study)
- c Pregnancy test should only be performed on FCBP. Urine pregnancy test is recommended and must be performed (and negative) within 7 days prior to starting study treatment and on day 77. Site may use serum pregnancy test if part of their procedures. For patients in the UK and France, urine pregnancy tests must also be performed every month or sooner while the patient is receiving G100.
- d Post-treatment biopsy should be done on Day 56 +/- 7 days for patients not receiving optional treatment #9. If the 9th dose is given, biopsy should be delayed to Day 63 to 77.
- e Patients should have all AEs reported for at least 30 days following the last dose of the G100 study agent. This includes those who withdraw early before completion of the study.
- f Thyroid function tests (including TSH) should be performed at screening in those patients being evaluated to participate and be randomized in Part 2 G100 vs. G100 plus pembrolizumab.
- g Patients will receive telephone follow-up or clinic visit every 8 to 12 weeks after disease progression until 1 year after first study injection. Follow-up will include vital status (survival), cancer status (e.g., lymphoma transformation), and post-treatment anti-cancer therapy including time to next treatment, treatment details, and clinical response. If the patient agrees, the site may periodically (e.g. every 2 to 4 months) contact the patient beyond 1 year to check on vital and cancer status.

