### 5.6.4 Progression-free Survival (PFS)

PFS is defined as time from date of first study treatment to date of first disease progression by irRC criteria, symptomatic deterioration, or death due to any cause, whichever occurs first. Progression-free survival (PFS) in months is calculated as: (date of first progression, symptomatic deterioration, or death (any reason) – date of first dose +1)/30.4375. The irRC modification requires a PD confirmation no less than 4 weeks from first documentation of progressive Disease (PD); once confirmed, the date of progression is defined as date of the first PD. In case of unconfirmed PD followed by symptomatic deterioration, the date of unconfirmed PD will be the date of progression. Patients without progression, symptomatic deterioration, or death are censored at the date of the last tumor assessment. If a patient begins a new anti-cancer therapy or has radiotherapy or surgery at a lesion site prior to confirmed progression (or death), the patient will be censored at the last assessment where the patient is documented as progression free prior to the intervention. Patients with two or more missing response assessments prior to a visit with progression (or death) will be censored at the last visit where the patient is documented to be progression free. Patients without disease assessment post-baseline will be censored at the first dose date. Table 7 below provides further details on how date of PFS event and date of PFS censoring are assigned.

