### 5.6.5 Overall Survival (OS)

Overall Survival (OS) is defined as the time from date of first study treatment to death due to any cause. Overall survival in months is calculated as:  $(\text{date of death} - \text{date of first dose}) + 1) / 30.4375$ . Patients who are alive at the end of study will be censored at the last date the patient is known to be alive or data analysis cutoff date, whichever is earlier.

Summary of OS including median, 95% CI, 25th and 75th percentiles, and range will be estimated using the Kaplan-Meier method. The corresponding 95% CI for median will be calculated using the Brookmeyer and Crowley method. The Kaplan-Meier survival curve will be displayed.

OS data will be presented in a data listing.

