### Partial Dates for Subsequent Therapy

Incomplete subsequent therapy dates will be imputed. Imputed dates will be used to determine Study Day.

Partial start dates will be imputed as follows:

1. Only the year is reported, with month and day missing: If the subject's last study treatment and subsequent therapy are in the same year, then the date of the last dose of study treatment will be used to impute the start date of the subsequent therapy.
2. The month and year are reported, with day missing: The first day of the month will be used to impute the start of the subsequent therapy.

Partial end dates will be imputed for non-ongoing therapies as follows:

1. Only the year is reported, with month and day missing: the earlier of December 31 or analysis cut-off date will be used to impute the end of the therapy.
2. The month and year are reported, with day missing: The last day of the month will be used to impute the end of the therapy.

End dates for ongoing therapies will be imputed to analysis cut-off date.

If an imputation results in an imputed start date after the stop date, set the date with more imputation to the one with less imputation.

Subsequent anti-cancer therapies will be summarized by part, treatment and will be presented in a listing.

- Any subsequent anti-cancer therapy
- Type of therapy
- Subsequent systemic therapy regimen/agents
- Best response
- Reason for discontinuation

Subsequent procedures and surgeries will be presented in a separate listing.

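### SAP 5.2 puts no bound on an imputed death date, so a year-only death can fall before a contact at which the patient was alive, or before first dose

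*SAP*

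**What the plan says.** SAP 5.2 (Missing Data) leaves adverse events, concomitant medication and subsequent therapy to their own sections and then sets a general rule, introduced by "For other analysis when necessary (e.g., OS analysis". Under it, a date that lacks only the day is placed mid-month, on the 15th. When the month is missing as well, the rule reads "dates without a specific day or month (i.e., 2010) will be assigned the 15th day of June". No condition is attached to either part.

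SAP 5.6.5 gives the endpoint: "Overall Survival (OS) is defined as the time from date of first study treatment to death due to any cause", computed in months as (death date minus first-dose date plus 1)/30.4375. The last date known alive appears there only as a censoring date: "Patients who are alive at the end of study will be censored at the last date the patient is known to be alive" or at the data cut-off, whichever is earlier.

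Death dates are used elsewhere too. In SAP 5.6.4, "PFS is defined as time from date of first study treatment to date of first disease progression by irRC criteria, symptomatic deterioration, or death" from any cause, whichever is first. SAP 5.6.3 ends duration of response and duration of clinical benefit at progression or death.

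The only repair rule for inconsistent imputed dates is in SAP 5.6.7, under partial dates for subsequent therapy. It begins "If an imputation results in an imputed start date after the stop date" and concerns therapy start and stop dates only. The protocol has no rule for partial death dates.

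**The concern.** A midpoint convention is reasonable when nothing else is known about a date. For a death something else is always known: the patient was alive at first dose and at every later contact. The SAP uses such information for its other partial dates. Subsequent-therapy dates are tied to the last study treatment and the analysis cut-off, and partial adverse-event dates are compared with first and last dose. The rule that dates deaths has no such anchor.

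A programmer who follows SAP 5.2 literally can therefore produce a death before a documented visit, a survival time of zero or less, or a death after the data cut-off. Because PFS takes whichever event comes first, an imputed death that falls before a progression recorded later in the same year would also become the PFS event.

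**Working it through.** The documents give no figure of their own here, so there is nothing to reproduce. The inputs are the SAP 5.2 rule, the SAP 5.6.5 formula and the contact schedule in the SAP Table 1 footnotes: "Patients will receive telephone follow-up or clinic visit every 8 to 12 weeks after disease progression until 1 year after first study injection". After that year contact is optional, for example every 2 to 4 months. All calendar dates below are assumed for illustration.

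**Size of the possible error**
- 15 June to 31 December is 199 days, or 199/30.4375 = 6.5 months. 1 January to 15 June is 165 days in a 365-day year. A year-only death can thus be dated up to 199 days early or 165 days late.
- With only the day missing, the largest early error is 31 − 15 = 16 days.

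**Individual records under the rule**
- First dose 9 January 2017, last seen alive 30 October 2017, death reported as 2017. The imputed death is 15 June, 137 days before the last contact. OS = (157 + 1)/30.4375 = 5.19 months. The feasible range, 31 October to 31 December, is 296/30.4375 = 9.72 to 357/30.4375 = 11.73 months.
- First dose 1 August 2017, last seen alive 1 November 2017, death reported as 2017. OS = (−47 + 1)/30.4375 = −1.51 months. The feasible range is 94/30.4375 = 3.09 to 153/30.4375 = 5.03 months.
- The formula gives exactly 0 for a first dose on 16 June of the death year and a negative value for any later first dose.

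**How often a year-only death would precede the last contact**

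Assume that death is uniform over a 365-day year and that the last contact is uniform over 0 to g days before death. For a gap of U days, the impossible ordering occurs when death falls more than U days after 15 June, so P = E[max(199 − U, 0)]/365.

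| Assumed g (days) | Calculation | P |
|---|---|---|
| 84 (12-week contacts kept) | (199 − 42)/365 = 157/365 | 0.43 |
| 120 (about 4 months) | (199 − 60)/365 = 139/365 | 0.38 |
| 365 (contact lapsed) | 199²/(2 × 365)/365 = 54.2/365 | 0.15 |

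For a day-missing date in a 31-day month with g = 84, P = 16²/(2 × 84)/31 = 0.05.

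**Average shift**

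Under the same uniform assumption, the mean error over all year-only deaths is (199 − 165)/2 = 17 days early.

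**The case against.** The strongest reply is that such records will be rare and will be caught. If the 8- to 12-week contacts are kept, a death is bracketed within about 12 weeks, and a year-only date is then unlikely. Fatal serious adverse events go to the sponsor at once (protocol 12.6), and on-study deaths need narratives (protocol 14.3.1). Case report forms are checked for logical consistency (protocol 16.0), with clarification forms for corrections (protocol 18.2). SAP section 1 leaves programming detail to the ADaM specifications and allows documented deviations. OS is an optional exploratory analysis (protocol 14.3.3), summarised only by Kaplan-Meier estimates. The Part 4 and Part 5 efficacy criteria rest on counts of responders and complete responses, which imputed death dates do not enter.

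Most of this stands as an argument about size. It also undercuts any single figure for frequency: the 43% presumes regular contact, the very setting in which year-only dates should be rarest, so the range down to 15% has to be shown with it. It does not supply a bound, however. Data queries may fail for late deaths learned at a distance. The permission to deviate leaves the replacement date to be chosen after the contradiction has been seen.

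A reader might also infer that the rule shortens OS materially overall, or visibly moves the Kaplan-Meier curves because the groups are small. The documents do not support either. The rule errs in both directions, with a mean of about 17 days early. They do not say how many deaths or partial death dates there are, so no effect on a curve can be calculated.

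**Conclusion.** Wrong as written, but minor. Applied literally, the rule can date a death before a documented live contact, by at most 199 days for year-only dates and 16 days for day-missing dates, and it can give a zero or negative OS. The same date carries into PFS, duration of response and duration of clinical benefit when death is the event.

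The conflict would affect about 15% to 43% of year-only deaths, given deaths uniform over the year and the assumed contact gaps. Those are shares of year-only deaths, not of all deaths. The number of year-only deaths is not stated and is probably small. The defect is impossible individual records in an exploratory, descriptive endpoint. It does not threaten the trial's safety or response conclusions.

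**What to change.** Add one sentence to SAP 5.2: an imputed death date is the later of the stated midpoint (the 15th of the month, or 15 June) and the day after the last date known alive, and no later than the end of the reported month or year and the data cut-off. Because the last date known alive cannot precede first dose, this also removes negative survival times. In the two examples above, OS becomes 9.72 and 3.09 months instead of 5.19 and −1.51.

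The version log shows the SAP as signed off, so a short addendum and a matching line in the ADaM specification would do. No new data are needed, and dates already consistent with the contacts and the cut-off do not change. There is a small downside: deaths moved to the floor sit at the earliest feasible day, so OS for those patients stays slightly conservative.

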## **5.3 Patient Disposition**

Patient disposition and the incidence of treatment discontinuation and study discontinuation (and the reasons for discontinuation) will be tabulated for all enrolled patients by part, treatment, and overall. The number and percentages of patients in each category will be reported. Patient disposition listing will be provided.

## **5.4 Protocol Deviations**

The clinical study team will define CSR reportable protocol deviations and major protocol deviations that will exclude a patient from Efficacy Evaluable population. The clinical study team will review all potential protocol deviations at regular time interval during study conduct and prior to database lock. Protocol deviations will be categorized by deviation type. CSR reportable protocol deviation and major protocol deviations that will exclude a patient from Efficacy Evaluable population will be flagged. The patient incidence of CSR reportable protocol deviations will be summarized by deviation type based on Safety population.

## **5.5 Demographics and Baseline Information**

### **5.5.1 Demographics and Baseline Characteristics**

Patient demographic and baseline characteristics include Age, Sex, Childbearing Potential for Female, Race, Ethnicity, Height, Weight, and ECOG Performance Status will be summarized by part, treatment, and overall, for Safety and Efficacy Evaluable population. A separate summary by treatment will be provided.

### **5.5.2 Cancer History**

Cancer history will be summarized by part, treatment, and overall, for Safety and Efficacy Evaluable population. The summary will include the following:

- Type of Lymphoma
- Histologic Type by WHO Classification at Diagnosis
- Did the WHO Classification Change?
- Histologic Type at Study Entry by WHO Classification
- Ann Arbor Stage at Diagnosis
- Did the Stage Change?
- Ann Arbor Stage at Study Entry

- Number of Nodal Sites
- Number of Index Lesions at Baseline
- Disease Status
- Tumor Growth / Progressive Disease at Study Entry

### **5.5.3 Medical and Surgical History**

Medical and surgical history will be listed based on Safety population.

### **5.5.4 Prior Anti-Cancer Therapy**

Prior anti-cancer therapy will be summarized by part, treatment, and overall, for Safety and Efficacy Evaluable population. A separate summary by treatment will be provided. The summary will include the following:

- Any Prior Therapy (Radiotherapy, Immunotherapy, Systemic Therapy, Other Therapy)
  - Type of Therapy
  - Intent of Treatment
  - Number of Any Prior Therapy
  - Number of Patients with Stem Cell/Bone Marrow Transplant
- Prior Systemic Therapy Regimen/Agents
  - Number of Prior Systemic Therapy
  - Best Response
  - Reason for Discontinuation from Prior Systemic Therapy Regimen

In addition, demographic and baseline characteristics, cancer history and anti-cancer therapy data will be presented in listings.

## **5.6 Efficacy Evaluation**

Unless otherwise specified, efficacy analyses will be performed by part, treatment, and overall. A separate summary by treatment will be provided. Efficacy evaluation will be provided for the Efficacy Evaluable population. Efficacy evaluation based on the Safety population will be provided as a supportive analysis.

### **5.6.1 Tumor Growth Rate**

At the baseline tumor assessment, the sum of the products of the two largest perpendicular diameters (SPD) of all index lesions is calculated. At each subsequent tumor assessment, the SPD of the index lesions and, new measurable lesions if any, are added to provide the total tumor burden:

$$\text{Tumor Burden} = \text{SPD index lesions} + \text{SPD new measurable lesions}$$

Post treatment initiation, spider plot (% change and change from baseline in SPD of index and new measurable lesions) for all visits will be presented for all lesion sites and abscopal sites. Waterfall plot (best % change and best change from baseline) will be presented for all lesion sites and abscopal sites.

Best percentage change in sum of tumor bi-dimensional products for abscopal lesions will be summarized by part, treatment, and overall.

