--	--

Immune Design

G100 (GLA-SE) and Pembrolizumab or Rituximab

Protocol IMDZ-G142; Version 04B, November 15, 2018

	
the examination of safety and dose effect. Treatment would be administered on the same treatment schedule as in Part 1 except that the G100 dose would be 20 µg of the GLA component. The dose will be administered to a single large target lesion or distributed among 2 or more lesions within the radiation field. If the target lesion(s) regresses, a different lesion within the radiation field will be chosen for treatment, if available. If the tumor mass has not regressed completely following 6 doses, treatment may continue for 3 additional weekly intratumoral doses (9 total).
 
Part 3, G100 Expansion of 20 µg Dose group: Following completion of enrollment of the Part 2 Patient Expansion With or Without Pembrolizumab group (as determined by Sponsor), and when at least 3 patients are enrolled in the Large Tumor Group with follow-up to at least Day 28, and contingent upon determining an acceptable safety profile following a review of G100 alone data, commencement of Part 3 will begin. Up to 25 patients with follicular NHL will be enrolled to receive local radiation therapy and intratumoral G100 at 20 µg/dose following the same treatment schedule as in Part 1 and Part 2 where G100 was administered alone. Large tumors are not required, and patients with any injectable tumor mass regardless of size may participate. Data from another study in sarcoma and early data from this trial have not demonstrated any safety concerns with the 20-µg dose level, and to date, all reported events considered at least possibly related to the study agent have only been grade 1 or 2. Compared to baseline, post-treatment tumor biopsies have demonstrated significant increases in immune infiltrates within the tumor of some patients suggesting that this dose level should be explored further. The dose will be administered to a single target lesion or distributed among 2 or more lesions within the radiation field. If the target lesion(s) regresses, a different lesion within the radiation field will be chosen for treatment, if available. If the tumor mass has not regressed completely following 6 doses, treatment may continue for 3 additional weekly intratumoral doses (9 total). Data will be monitored continuously for safety, clinical effect, and exploratory biomarkers.
 
Part 4, G100 at 20µg/lesion Into Single Or Multiple Tumor Masses Plus Pembrolizumab: Data from Parts 1-3 of this study demonstrate that intratumoral G100 at the highest dose examined (20µg) has been well-tolerated with only grade 1 or 2 related AEs and no DLTs reported with its use. This higher dose has been associated with increased numbers of infiltrating CD8 T cells into the tumor (TILs), and greater numbers of CD8 TILs have been statistically associated with the development of objective clinical responses. In Part 2, the combination of G100 (10 µg) and pembrolizumab was well-tolerated without new or unexpected toxicities, and the addition of pembrolizumab resulted in more clinical responses, deeper abscopal tumor shrinkage, and a higher number of tumor infiltrating CD8 T cells. Therefore Part 4 will examine the 20µg dose of G100 in 1 or more tumor lesions (up to 4 lesions) plus pembrolizumab in order to establish safety and examine clinical and biomarker responses in patients receiving increasing total systemic doses of G100.

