4.4 Rationale for G100 Therapy

Intratumoral administration of TLR4 agonists can activate local DCs and other immune cells to react to local cancer cells despite the immunosuppressive nature of the tumor microenvironment. This approach has the potential to stimulate immune responses against known “specific” as well as previously unrecognized “endogenous” tumor antigens. This locally generated anti-tumor response would be expected to result in a systemic immunity and lead to regression of distal untreated lesions (abscopal response). In preclinical models and in ongoing clinical studies of Merkel cell carcinoma and sarcoma patients, intratumoral G100 has demonstrated early evidence of clinical activity with a reasonable safety profile. In this trial, intratumoral G100 therapy of patients with follicular NHL will be examined. These malignancies are known to contain tumor-specific antigens and have demonstrated responsiveness to active immunotherapy approaches with idiotype vaccines, with intratumoral DCs and with intratumoral CpGs. This may indicate that NHL are an ideal indication to investigate this approach.

This study will be performed in multiple parts. In Part 1, Dose Escalation, the safety and tolerability of 5 μ g or 10 μ g of G100 will be investigated following standard local radiation

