4.6 Rationale for Rituximab Therapy and Proposed Schedule

Rituximab either as a single agent or in combination with other agent(s) has become an essential treatment and a backbone of therapies used to treat follicular lymphomas and other B cell malignancies. The clinical anti-tumor activity of this anti-CD20 antibody appears to derive from its ability to facilitate antibody-dependent cellular cytotoxicity (ADCC), directly inducing apoptosis of lymphoma cells (studies with cross-linked antibody), and activating complement dependent cytotoxicity. ([Rituximab label 2010](#); [Hsu 2002](#))

[figure not shown]
The mechanism of action of G100 complements that of rituximab. ADCC requires the presence of activated NK cells, macrophages and other phagocytic cells. G100 releases cytokines and can attract and increase the number of activated NK and other phagocytic cells in the tumor microenvironment ([Figure 14](#)). In clinical studies of intratumoral G100 in patients with sarcoma, G100 was associated with an increase of inflammatory macrophages of M1 phenotype, indicating an increased activity ([Seo 2017](#)). Preliminary nanostring gene expression analysis using tumor biopsy collected from FL patients before or after G100 treatment showed induction of genes associated with NK cell function, including FcgR2A, FcgR3A, 2B4, Granzyme A, etc. As shown in [Figure 15](#), heatmap analysis of genes from two representative patients shows higher levels of genes expression of multiple NK cell receptors. This data would support the potential synergy between G100 and rituximab. Further testing using PBMC from healthy donors and rituximab-coated target Raji cells showed that pre-incubation of PBMC with GLA (0.2 or 1 μ g/mL for 48hr) significantly enhanced the lysis of target cells at different concentrations of rituximab ([Figure 16](#)).

Immune Design

G100 (GLA-SE) and Pembrolizumab or Rituximab

[figure not shown]
Protocol IMDZ-G142; Version 04B; November 15, 2018

Figure 14: G100 Increases NK Cells In The Tumor Microenvironment

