10.3.3 Visit 3 and Visit 4: Radiation Therapy (Day 0 and Day 1)

Patients receive local radiation therapy to tumor mass identified for intratumoral treatment. Standard 2Gy each day \times 2 is recommended. Treatment plan will be determined by the treating radiation therapist. Changes in doses should be discussed with Immune Design.

As part of this study, the injected lesion(s) is followed for local effect, and untreated, abscopal lesions are followed for systemic treatment effect. Therefore the G100 treated / irradiated lesion should be one of the Index (target) lesions followed for response. In addition, the radiation treatment field should be reviewed by the radiation therapist to confirm the identity of all irradiated lesions and untreated “abscopal” lesions to be used to follow treatment response. (For the purpose of this study, abscopal tumor site refers to a lesion that is not irradiated or injected / treated that can be followed for shrinkage that would indicate a systemic immune effect)

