### 2.2 Secondary Objectives

- To assess clinical responses by Immune-related Response Criteria (irRC) using bi-dimensional measurements and time to progression (TTP) as a preliminary indication of efficacy.  
For comparison, clinical responses will also be assessed by the International Working Group response criteria and Lugano criteria for lymphomas (Cheson 2014) for Part 4 & Part 5 patients.
- To assess abscopal tumor responses in non-treated, distal tumor sites

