### **5.6.8 Immune Response and Biomarker Analyses**

All patients who have received at least one injection of G100 and have available immunohistochemistry (IHC), nanostring, or T cell receptor (TCR) data will be included in the biomarker analysis.

Anti-tumor cellular immunity (CD4, CD8 T cell, CD20, CD68, NKp46, FoxP3, CD8/CD4 ratio, CD8/FoxP3 ratio) by immunohistochemistry (IHC) will be explored. Post/pre treatment ratio will be summarized by treatment, and by subgroups of interest (irPR vs non-responder, pre-TLR4 $\geq$ 50% vs <50%, treatment naïve, relapsed/refractory patients, prior line of therapy 0-2 vs  $\geq$ 3). Post and pre treatment values will be compared using signed-rank test to identify significant changes post treatment. Association between clinical endpoints (irPR, irPR+MR, irPR+MR+SD, abscopal best % change better than -25%) and cellular immunity by immunohistochemistry will be explored using a logistic regression model for all dosed patients, and by treatment. Association between response (irPR) and pre-treatment TLR4 using different cutoffs will be presented in 2x2 tables and the proportion of response will be compared between TLR4 high and TLR4 low patients using Barnard's unconditional exact test. Comparison of post treatment change in immunohistochemistry will be explored between G100 monotherapy 10  $\mu$ g and G100 monotherapy 20  $\mu$ g patients.

Association between clinical response and nanostring genes (NK, M1 Markers, M2 Markers, and other genes of interest) using PBMC and tumor samples will be explored using a logistic regression model that includes  $\log_2$  transformed nanostring data. Post/pre mean expression ratio (as antilogarithm of the means of ( $\log_2$  post –  $\log_2$  pre)) for responder and non-responder, odds ratio, and nominal and adjusted p-values will be presented. Adjusted p-value is adjusted using False Discovery Rate (FDR) method. Ten most upregulated and ten most downregulated immune-related genes will be presented, with post/pre mean expression ratio and p-value from signed-rank test. Further, ten most highly differentially induced immune-related genes in clinical responders versus non-responders will be explored.

T cell receptor (TCR) clones not detectable at baseline in tumor/PBMC but become detectable or increased post-treatment in tumor/PBMC will be explored.

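### The pooled marker-response models in SAP 5.6.8 state no treatment term, and the overall abscopal row in SAP 5.6.1 mixes G100 alone with G100 plus a systemic antibody

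*SAP*

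**What the plan says.** The secondary objective for all parts is "To assess abscopal tumor responses in non-treated, distal tumor sites" (SAP 2.2). Protocol 10.3.3 defines the term: an "abscopal tumor site refers to a lesion that is not irradiated or injected / treated", one "that can be followed for shrinkage that would indicate a systemic immune effect". Protocol 4.4 gives the mechanism: the local anti-tumor response to G100 "would be expected to result in a systemic immunity and lead to regression of distal untreated lesions (abscopal response").

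SAP 5.6.1 states: "Best percentage change in sum of tumor bi-dimensional products for abscopal lesions will be summarized by part, treatment, and overall". SAP 5.6 adds a separate by-treatment summary for efficacy in general.

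SAP 5.6.8 relates several clinical endpoints, among them an abscopal best change better than -25%, to IHC markers: the association with "cellular immunity by immunohistochemistry will be explored using a logistic regression model for all dosed patients, and by treatment". The next paragraph of 5.6.8 fits logistic models of clinical response on log2 nanostring expression. It mentions neither a split by treatment nor a treatment term. SAP 7 names covariates only for the comparison of 10 µg with 20 µg G100 monotherapy.

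In the Part 4 rationale (Protocol 3.1 and 6.1, repeated in SAP 3.1), the documents report from Part 2 that "the addition of pembrolizumab resulted in more clinical responses, deeper abscopal tumor shrinkage, and a higher number of tumor infiltrating CD8 T cells".

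**The concern.** A confounder in a marker-response model is something related to both the marker and the response. By the documents' own account, adding pembrolizumab moved response, abscopal shrinkage and CD8 infiltration in the same direction. A model that pools G100 alone with G100 plus pembrolizumab and has no treatment term can therefore return a positive CD8-response association even if CD8 tells nothing about response within either regimen. The false-discovery-rate adjustment planned for the nanostring p-values deals with the number of tests, not with this.

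The overall abscopal row has a related weakness. Distal lesions in the Part 2 combination arm and in Part 4 are exposed to intravenous pembrolizumab from Day 14, before the first restaging images at Day 56 or later. In Part 5 they are exposed to rituximab, of which Protocol 4.6 says: "The clinical anti-tumor activity of this anti-CD20 antibody appears to derive from its ability to facilitate antibody-dependent cellular cytotoxicity". A figure pooled over these groups and G100 alone does not describe any one regimen.

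What is at stake is how the exploratory results are read. The Part 4 rationale already cites an association between CD8 infiltration and response, so findings of this type do inform development.

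**Working it through.** **1. Planned make-up of the pooled group.** The inputs are Part 1 up to 12 (Protocol 7.0); Part 2 randomized 12 + 12, Large Tumor up to 4, Part 3 up to 25 and Part 4 at least 22 (SAP 3.4); and Part 5 12-24 plus 20 (Protocol 7.0).

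Check against the plan: 12 + 24 + 4 + 25 = 65, which matches the 65 stated for Parts 1-3 in SAP 3.4.

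G100 without a systemic antibody: 12 + 12 + 4 + 25 = 53. This is a ceiling. Protocol 14.2 expects 18 such patients in Part 1 and the Part 2 randomized group, which gives 18 + 4 + 25 = 47.

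Share of the overall row that also receives an antibody, using 53:
- Parts 1-3: 12/65 = 18.5%
- Parts 1-4: (12 + 22)/87 = 34/87 = 39.1%
- Parts 1-5 with 32 to 44 patients in Part 5: 66/119 = 55.5% to 78/131 = 59.5%

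**2. Effect on an overall abscopal rate.** The documents give no abscopal rates, so these are assumptions. Take 20% on G100 alone and 40% on the combination, Parts 1-4: (53 × 0.20 + 34 × 0.40)/87 = 24.2/87 = 27.8%. With 30% or 60% on the combination, the pooled rate is 23.9% or 35.6%. The pooled value depends on the enrollment mix.

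**3. Effect on the pooled odds ratio.** Let r0, r1 be the response rates and m0, m1 the proportions with a high marker, on G100 alone and on the combination. Marker and response are independent within each regimen, so the within-treatment odds ratio is 1.0. With group sizes n0, n1:

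- high marker, responder: a = n0·m0·r0 + n1·m1·r1
- high marker, non-responder: b = n0·m0·(1-r0) + n1·m1·(1-r1)
- low marker, responder: c = n0·(1-m0)·r0 + n1·(1-m1)·r1
- low marker, non-responder: d = n0·(1-m0)·(1-r0) + n1·(1-m1)·(1-r1)
- pooled OR = ad/(bc)

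Worked case with equal groups, r = 0.2 and 0.4, m = 0.3 and 0.6: a = 0.06 + 0.24 = 0.30; b = 0.24 + 0.36 = 0.60; c = 0.14 + 0.16 = 0.30; d = 0.56 + 0.24 = 0.80. OR = 0.24/0.18 = 1.33.

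| r0, r1 | m0, m1 | Equal groups | 53 and 34 (Parts 1-4) | 53 and 12 (Parts 1-3) |
|---|---|---|---|---|
| 0.2, 0.4 | 0.3, 0.6 | 1.33 | 1.34 | 1.24 |
| 0.2, 0.5 | 0.3, 0.6 | 1.49 | 1.50 | 1.36 |
| 0.1, 0.4 | 0.3, 0.7 | 1.92 | 1.97 | 1.77 |

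If m0 = m1, the pooled OR is 1.00 whatever the response rates. In the randomized part, pre-treatment markers should differ between arms only by chance. The bias therefore mainly concerns post-treatment and post/pre measures, and comparisons across parts with different eligibility.

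**4. Size against noise.** With 53 and 34 patients, and IHC assumed available for all, the approximate 95% interval (Woolf) is 0.5 to 3.4 around 1.34 and 0.7 to 5.5 around 1.97.

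**The case against.** - **The stratified output is already planned.** This stands. The abscopal summary, the efficacy summaries in general and the IHC models are all also given by treatment. A reader might infer that the SAP only pools, and that is wrong. What remains is the extra overall row, the extra all-dosed IHC model, and the nanostring models, where no split is stated. A by-treatment model may rest on as few as 12 patients, as in one Part 2 arm taken alone, so a reader may well turn to the pooled one.
- **Nothing attributes the pooled result to G100.** This stands. A reader might infer that antibody effects will be reported as G100 effects. No text says so: the objective names no agent, Protocol 10.3.3 speaks of a systemic immune effect, and the Part 4 rationale credits the deeper abscopal shrinkage to pembrolizumab.
- **Abscopal is defined by local treatment.** This stands. A reader might infer that Part 5 falls outside the abscopal objective because rituximab reaches every lesion. The definition turns on irradiation and injection, and the Part 4 and Part 5 biopsy notes contrast G100-treated with abscopal sites. Protocol 8.1.4 and the Part 5 visit procedures already speak of non-injected lesions. What is limited in the combination groups is attribution.
- **The rituximab component may be empty.** This is possible. SAP 9 reports termination by the sponsor, and the SAP exposure and adverse-event tables list no rituximab summaries. Part 5 enrollment is not stated. The pembrolizumab point holds without it, as the Parts 1-3 column of the table shows.
- **The rates are assumed, the intervals include 1, and the work is exploratory.** This is all true and it limits the weight of the point. SAP 8 declares nominal p-values outside the nanostring analysis, and no decision rule in SAP 3.4 uses these models. It is still not a reason to leave out a known confounder that costs one model term to handle.

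**Conclusion.** The point holds as a minor one. As written, the all-dosed IHC models and the nanostring response models can show a marker-response association produced only by combining regimens, because the documents report that pembrolizumab raised both CD8 infiltration and response. The illustrative distortion is a pooled odds ratio of about 1.3 to 1.9 where the within-treatment value is 1.0. This rests on assumed response rates and marker prevalences, and it vanishes if marker prevalence does not differ by treatment.

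The overall abscopal row mixes regimens in proportions set by enrollment. No part has an antibody-alone arm, so the combination groups cannot isolate what G100 contributes to distal shrinkage. Part 2 can describe the increment from pembrolizumab, since that contrast is randomized. Direct evidence on a G100 abscopal effect comes only from the G100-alone groups, and those patients also had low-dose local radiation. The documents do not support a charge that the SAP misattributes the effect or omits by-treatment results.

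**What to change.** - **SAP 5.6.8:** in the all-dosed IHC models and the nanostring response models, add treatment group (G100 alone, plus pembrolizumab, plus rituximab if any patients were enrolled) as a covariate or stratum, and state this in SAP 7. The choice of estimation method for sparse data can be left to the analyst.
- **SAP 5.6.1:** drop the overall abscopal row, or footnote it as a mix of regimens. Base any statement about a G100 abscopal effect on the G100-alone groups, which the by-treatment summary already provides.

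The cost is a few lines of SAP text, one model term and a slight loss of precision in exploratory models. No new data or visits are needed.
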